15.0 Product Information

- 15.1 Serum-Derived Bovine Immunoglobulin Protein Isolate (SBI, EnteriaGam™) or matching placebo

- 15.11 **Background:** Serum-derived bovine immunoglobulin protein isolate is an orally administered prescription medical food containing a proprietary formulation of bovine immunoglobulin (> 50% IgG) and other serum proteins. The product is manufactured in accordance with Good Manufacturing Practices and FDA guidelines for medical food ingredients.

It is indicated for the nutritional management of a patient with enteropathy who, because of therapeutic or chronic medical needs, has limited or impaired capacity to ingest, digest, absorb, or metabolize ordinary foodstuffs or certain nutrients.

Serum-derived bovine immunoglobulin protein isolate must be non-digestible and able to reach the gastrointestinal tract to benefit an immunocompromised or otherwise dysfunctional GI mucosa. In humans, SBI is used as a passive, immunity-enhancing nutrient to augment traditional medications. Clinical studies have provided evidence that SBI lowers total and LDL cholesterol in patients with mild hypercholesterolemia, reduces symptoms of gastroenteropathy in IBS-D and HIV+ patients, increases GI absorption, and decreases GI permeability.

15.12 **Formulation:** Serum-derived bovine immunoglobulin protein isolate is a light-colored powder composed of finely ground flakes of immunoglobulin and other serum proteins (ie, transferrin, albumin, alpha and beta proteins). Serum-derived bovine immunoglobulin protein isolate is supplied in individual packets containing 5 grams of SBI and the following ingredients: dextrose, orange (natural and artificial flavors) and coloring (Yellow #6). Matching placebo packets will be supplied and will appear identical to SBI with respect to volume, appearance, and taste. The ingredients of the placebo will include dextrose, orange (natural and artificial flavors) and coloring (Yellow #6).

15.13 **Preparation and storage:** Blinded investigational product (SBI or matching placebo) will be packaged in kits containing 5 grams of SBI per each packet or as matching placebo packets. An investigational product kit with a unique ID number will contain 14 packets (7 days of required product) and 4 extra packets (18 packets total) to accommodate the flexibility with return visits. Packets are to be stored at 20-25°C (68-77°F), with excursions permitted between 15-30°C (59-86°F).

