16.0 Statistical Considerations and Methodology**16.1 Overview**

This randomized study is pilot in nature insofar as its main goal is to provide preliminary data to put in place the groundwork for a much larger, definitive study. The primary aim of the current study is to compare the time-to-quality of life (QOL) improvement from baseline in postoperative gynecological cancer patients who are receiving oral SBI vs. placebo. If this trial can provide preliminary evidence that oral SBI significantly improves the time-to-QOL improvement as compared to placebo, further study would be warranted to determine whether the administration of oral SBI shortens the time-to-chemotherapy administration post-operatively in ovarian cancer patients. In addition to time-to-QOL improvement, this trial will also compare adverse event rates, complication rates, QOL from validated QOL tools, and intervention compliance between patients receiving oral SBI vs. placebo.

- 16.11 **Primary Endpoint and Statistical Design:** To compare the time-to-QOL improvement from baseline in postoperative gynecological cancer patients who are receiving oral SBI vs. placebo.

Final Analysis:

The primary goal of this trial is to compare the oral SBI arm (experimental) to the placebo arm (standard), where the alternative hypothesis is that the experimental arm has a shorter time to QOL improvement from baseline as compared to the standard arm. For this primary endpoint, the total score of the 14-item Postoperative Quality of Life (PQL) tool [15] will be used, where the total score could range from 0 to 140 (0 being the worst and 140 being the best). These scores will be converted to the percentage scale, where a score of 140 will

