be converted to 100 and a score of 0 will remain as 0. This QOL will be measured weekly for the entire 12 week length of the study and at the end of the intervention. QOL improvement will be defined as at least a 10 point increase in the QOL score from baseline, on the percentage scale. This 10 point change represents a clinically meaningful improvement in QOL based on work done by Jeff Sloan [17]. The date at which the QOL score is first known to increase by at least 10 from baseline (on the 100 point scale), will be considered the event date for the purpose of analysis. Patients without at least a 10 point increase in QOL from baseline, will be censored on their last QOL evaluation date up to a maximum of 12 weeks. We will enter a total of 70 evaluable patients (35 per arm) using a 1:1 randomization scheme. The primary analysis will be a comparison of oral SBI vs. placebo using a two-sided log-rank test between the 2 Kaplan-Meier curves [18]. This analysis will take place after an approximate 16 month accrual period, and after 66 total events across both arms combined (which should happen after about 12 weeks of follow-up in all evaluable patients). Additionally, we assume a constant accrual rate over the course of the study, and that no patients will drop-out of the study, since historically the lost to follow-up rate is <1%. To determine the appropriate sample size of 35 evaluable patients per arm, we assumed exponential survival and that the median time-to-QOL improvement is around 3 weeks in the oral SBI arm and 6 weeks in the placebo arm (HR=2). This hazard ratio is based on our institution's data which shows that patients often begin postoperative chemotherapy 6 weeks after surgery. These assumptions yield 80% power to detect a significant difference between the arms using a 2-sided log-rank test at alpha=0.05. All patients who meet the eligibility criteria, sign the consent form, and are randomized, will be considered evaluable for this endpoint. All eligible patients will be followed a maximum of 12 weeks. If the 2-sided log-rank test p-value is < 0.05 showing significantly shortened time-to-QOL improvement in the oral SBI arm as compared to placebo, further study will be warranted. Of course, any final decisions will be based on all primary and secondary endpoints.

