16.62 **Intervention Compliance:** Intervention compliance will be assessed using the Compliance Questionnaire in Appendix V. The frequency and percentage for each Compliance Questionnaire category will be summarized descriptively by cycle and by intervention arm. In addition, cycle by cycle compliance data will be compared between the 2 arms using a Chi-square test.

16.63 **Quality of Life:** QOL will be measured with 3 QOL tools. For the primary endpoint, the total score from the 14-item Postoperative Quality of Life (PQL) tool [15] (Appendix II) will be used (16.11). As a secondary analysis, all 14 of the individual items from the PQL tool (Appendix II), along with the 4 additional items after the PQL questions (Appendix II) will be analyzed and compared between the 2 intervention arms. In addition, the time-to-QOL improvement will be compared between the 2 arms for any increase (> 0) from baseline for the total score from the PQL tool. This will be done descriptively, and using a Kaplan-Meier analysis [18], where any increase in the QOL from baseline will represent an event. QOL will also be measured using the Uniscale (Appendix III), and the previously-validated Symptom Distress Scale (SDS; Appendix IV). These QOL tools will measure QOL at baseline, every week up to 12 weeks post-randomization, and at the end of intervention. Differences between post-randomization and baseline QOL scores will be analyzed and compared between the 2 arms using a Wilcoxon Rank-sum test. Also, other graphical and statistical methods will be used to compare the QOL and time-to-QOL improvement between the 2 arms. As an exploratory analysis, we will also collect QOL data on patients who do not start intervention/placebo or discontinue intervention/placebo early and are willing to be followed per the test schedule (Section 4). This analysis will be descriptive in nature to see if these patients have a poorer QOL than patients who stay on study.

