Appendix II Postoperative Quality of Life Questionnaire

Name and
Patient number _____ **Date** _____

The following questions are designed to gauge your current quality of life. Circle the answer that best indicates how you feel.

1. Quality of Life (0 = worst; 10 = best)

0 1 2 3 4 5 6 7 8 9 10

2. Quality of Health (0 = worst; 10 = best)

0 1 2 3 4 5 6 7 8 9 10

3. Level of Energy (0 = worst; 10 = best)

0 1 2 3 4 5 6 7 8 9 10

4. Pain at Rest

No Pain										Worst pain
0	1	2	3	4	5	6	7	8	9	10

5. Pain at Current Maximum Level of Activity

No Pain										Worst pain
0	1	2	3	4	5	6	7	8	9	10

6. Severity of Nausea or Vomiting

No nausea or vomiting										Worst nausea or vomiting
0	1	2	3	4	5	6	7	8	9	10

7. Fatigue

No Fatigue										Worst fatigue
0	1	2	3	4	5	6	7	8	9	10

8. How close is your bowel function to normal? (0 = most abnormal; 10 = normal)

0 1 2 3 4 5 6 7 8 9 10

9. How close are you to overall normal functioning for you? (0 = most abnormal; 10 = normal)

0 1 2 3 4 5 6 7 8 9 10

10. How close are you to your normal ability to get around the house? (0 = most abnormal; 10 = normal)

0 1 2 3 4 5 6 7 8 9 10

11. How close are you to your usual level of leisure activity? (0 = most abnormal; 10 = normal)

0 1 2 3 4 5 6 7 8 9 10

12. At what level is your sexual activity compared with normal? (0 = most abnormal; 10 = normal)

0 1 2 3 4 5 6 7 8 9 10

13. What is your current level of happiness: (0=sad; 10=happy)

0 1 2 3 4 5 6 7 8 9 10

14. What is your satisfaction with your overall level of medical care, including and since any surgery? (0=dissatisfied; 10=100% satisfied)

0 1 2 3 4 5 6 7 8 9 10

Additional Questions related to Quality of Life Post-surgery

1. Level of sleepiness

Totally alert	Very sleepy
0 1 2 3 4 5 6 7 8 9 10	

2. How many times per day on average did you experience nausea or vomiting?

Never 1-2 times 3-5 times > 5 times

3. How many times per day on average did you have a bowel movement

None 1 time 2-3 times 3-5 times > 5 times

Type 6		Fluffy pieces with ragged edges, a mushy stool
--------	--	--

Type 7		Watery, no solid pieces. Entirely Liquid
--------	--	--

4. What picture represents the typical bowel movement you had over the past 7 days. Please place an “X” over the appropriate picture.

Bristol Stool Chart

Type 1		Separate hard lumps, like nuts (hard to pass)
Type 2		Sausage-shaped but lumpy
Type 3		Like a sausage but with cracks on the surface
Type 4		Like a sausage or snake, smooth and soft

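### The bowel-movement frequency item in Appendix II has answer boxes that overlap at three a day; the cost is a small loss of sensitivity in one secondary comparison

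*Combined protocol and SAP*

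**What the plan says.** The four additional questions follow the 14 PQL items in Appendix II. The third asks "How many times per day on average did you have a bowel movement" and prints five answers: "None 1 time 2-3 times 3-5 times > 5 times". The question just above it, on nausea or vomiting, prints "Never 1-2 times 3-5 times > 5 times", which gives each whole number exactly one box.

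Section 16.63 says that the individual PQL items, "along with the 4 additional items after the PQL questions (Appendix II) will be analyzed and compared between the 2 intervention arms". Later in the same section the plan adds: "Differences between post-randomization and baseline QOL scores will be analyzed and compared between the 2 arms using a Wilcoxon Rank-sum test". The booklet is completed at baseline and weekly (Section 4.0).

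The primary endpoint in Section 16.11 does not use this question. There, "the total score of the 14-item Postoperative Quality of Life (PQL) tool [15] will be used". Neither Section 16 nor Appendix II says how an answer of three a day is to be recorded or scored.

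**The concern.** A frequency question needs boxes that do not overlap. Here a patient with three movements a day can correctly tick either of two neighbouring boxes. The question is repeated weekly, so the same patient may tick one box at baseline and the other later. The data would then show a one-category change when nothing had changed.

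The item bears on the product's rationale. Section 1.4 cites a fall from 5.7 to 2 bowel movements per day in a small HIV enteropathy study, and the ambiguous boundary lies inside that range. This is also the only one of the 18 PQL and additional items that asks for stool frequency. At stake is the precision of one secondary comparison in a pilot whose forms may be carried into a larger study.

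**Working it through.** The plan gives no power, error rate or distribution for this item, so there is no figure of its own to reproduce. The check has three parts.

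**1. Does the overlap exist, and where?** Each whole-number count is mapped to the printed boxes:

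| Count per day | Bowel-movement item | Nausea/vomiting item |
|---|---|---|
| 0 | None | Never |
| 1 | 1 | 1-2 |
| 2 | 2-3 | 1-2 |
| 3 | **2-3 and 3-5** | 3-5 |
| 4, 5 | 3-5 | 3-5 |
| 6, 7 | >5 | >5 |

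Only three a day is ambiguous, and only between two adjacent categories. The nausea/vomiting item has no such count.

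**2. How much sensitivity is lost?** From the plan: 35 evaluable patients per arm (Section 16.11) and a Wilcoxon rank-sum test (Section 16.63). Assumed: independent Poisson counts, a two-sided 5% level, one time point, and a patient at three choosing either box with probability 0.5. There were 3,000 simulated trials per setting.

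The share at exactly three is exp(-m) × m³ / 6 for mean m. This gives 0.126 at m = 1.5, 0.180 at m = 2, 0.214 at m = 2.5 and 0.224 at m = 3.

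| Means (arm vs arm) | Three always in 2-3 | Three always in 3-5 | Random choice |
|---|---|---|---|
| 2 vs 2 (no effect) | 0.047 | 0.047 | 0.045 |
| 2 vs 3 | 0.692 | 0.676 | 0.681 |
| 1.5 vs 2.5 | 0.787 | 0.777 | 0.788 |

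Boxes of 2-3 and 4-5 correspond to the first rule. The loss from random choice is 0.692 - 0.681 = 0.011 in one setting and 0.787 - 0.788 = -0.001 in the other. The simulation error of one entry is about √(0.68 × 0.32 / 3000) = 0.0085, so both are near the noise of the method. Across a wider set of assumed means the loss ran from 0 to about 3 points. For change from baseline it could not be told apart from simulation error. The type I error is not inflated.

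**3. Would merging the two boxes in the analysis repair it?** Merging puts two, three, four and five a day into one category. Under the same assumptions:

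| Means | Overlap left alone | Boxes merged | Lost by merging |
|---|---|---|---|
| 2 vs 3 | 0.68 | 0.58 | 0.10 |
| 1.5 vs 2.5 | 0.79 | 0.71 | 0.08 |
| 3 vs 4.2 | 0.67 | 0.60 | 0.07 |
| 2.5 vs 3.7 | 0.74 | 0.65 | 0.09 |
| 3 vs 4.5 | 0.84 | 0.78 | 0.06 |

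Merging costs roughly 6 to 10 points to recover at most about 3.

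**The case against.** The strongest reply is that this is a slip on a form with almost no consequence. Most of that stands. The item is one of 14 + 4 = 18 compared in a secondary analysis, and the computed loss is small.

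A reader might infer that the trial has few direct measures of bowel function, so that noise here is costly. The documents do not support that. PQL item 8 rates closeness to normal bowel function from 0 to 10 and is part of the primary total. Additional question 4 records stool form on the Bristol chart. The Symptom Distress Scale in Appendix IV has a bowel section. Section 10.6 requires graded diarrhea at each evaluation and the number of stools per day at baseline.

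A reader might also infer bias between the arms. Section 15.12 argues against this: "Matching placebo packets will be supplied and will appear identical to SBI with respect to volume, appearance, and taste". Blinded patients have no reason to resolve the ambiguity differently by arm.

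It can also be said that no change analysis is specified for this item by name. The Wilcoxon sentence refers to QOL scores and follows the text on the Uniscale and Symptom Distress Scale. That is fair: applying it to this item is a natural reading, not a stated one. The between-arm comparison itself is stated, and the overlap affects it either way.

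Finally, the question asks for an average. Boxes of 2-3 and 4-5 alone would leave 3.5 without a box, so a corrected form also needs a rounding instruction.

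**Conclusion.** The overlap is real and in the current text. It affects an item that the plan compares between arms, and nothing in the plan resolves it. It is a minor point. The expected effect is a loss of about 0 to 3 points of power in one secondary comparison, plus some spurious one-category changes among patients who average three a day. The primary endpoint, its sample size and the type I error are untouched, and no bias between arms is expected.

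The size rests on assumed Poisson counts with about 13% to 22% of patients at exactly three a day in the settings tabulated in part 2. The documents give no distribution, so the true share may differ. It would be too strong to call the outcome misclassified as a whole: only answers at three a day are ambiguous, and they can move by only one category.

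**What to change.** **Before booklets are issued:** make the options mutually exclusive in Appendix II and in the printed booklet, for example '2-3 times' and '4-5 times'. Add an instruction to round the average to the nearest whole number. The cost is a reprint, because Section 4.0 requires the official booklets and does not accept copies.

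**If booklets are already in use:** leave the form unchanged, since a mid-study change would make later answers not comparable with baseline. Keep the five ordered categories in the main comparison, and state in the report that the boundary at three a day is ambiguous. Do not merge the two boxes there. This costs one sentence in the analysis plan and one in the report.

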Appendix III UNISCALE – Patient Form

Patient Name: _____

Date: _____

Patient Number: _____

Directions: Please circle the number (0-10) best reflecting your response to the following question that describes your feelings during the past week, including today.

How would you describe your overall Quality of Life?

0	1	2	3	4	5	6	7	8	9	10
As bad										As good
as it										as it
can be										can be

Appendix IV SYMPTOM DISTRESS SCALE (SDS)

Each of the following sections lists 5 different statements. Think about what each statement says, and then place a circle around the one statement that most closely indicates how you have been feeling during the past 7 days. Please circle one statement for each section.

Appetite

1. I have my normal appetite
2. My appetite is usually, but not always, pretty good
3. I don't really enjoy my food like I used to
4. I have to force myself to eat my food
5. I cannot stand the thought of food

Insomnia

1. I sleep as well as I always have
2. I have occasional spells of sleeplessness
3. I frequently have trouble getting to sleep and staying asleep
4. I have difficulty sleeping almost every night.
5. It is almost impossible for me to get a decent night's sleep

Pain (a):

1. I almost never have pain
2. I have pain once in a while
3. I frequently have pain-several times a week
4. I am usually in some degree of pain
5. I am in some degree of pain almost constantly

Pain (b)

1. When I do have pain, it is very mild
2. When I do have pain, it is mildly distressing
3. The pain I do have is usually fairly intense
4. The pain I have is usually very intense
5. The pain I have is almost unbearable

Fatigue

1. I am usually not tired at all
2. I am occasionally rather tired
3. There are frequently periods when I am quite tired
4. I am usually very tired
5. Most of the time, I feel exhausted

Bowel

1. I have my normal bowel pattern
2. My bowel pattern occasionally causes me some discomfort
3. I frequently have discomfort from my present bowel pattern
4. I am usually in discomfort because of my present bowel pattern
5. My present bowel pattern has changed drastically from what was normal for me.

Concentration

1. I have my normal ability to concentrate
2. I occasionally have trouble concentrating
3. I often have trouble concentrating
4. I usually have at least some difficulty concentrating
5. I just can't seem to concentrate at all

Appearance:

1. My appearance has basically not changed
2. My appearance has gotten a little worse
3. My appearance is definitely worse than it used to be, but I am not greatly concerned about it
4. My appearance is definitely worse than it used to be, and I am concerned about it
5. My appearance has changed drastically from what it was

Breathing:

1. I usually breathe normally
2. I occasionally have trouble breathing
3. I often have trouble breathing
4. I can hardly ever breathe as easily as I want
5. I almost always have severe trouble with my breathing

Outlook:

1. I am not fearful or worried
2. I am a little worried about things
3. I am quite worried, but unafraid
4. I am worried and a little frightened about things
5. I am worried and scared about things

Cough:

1. I seldom cough
2. I have an occasional cough
3. I often cough
4. I often cough, and occasionally have severe coughing spells
5. I often have persistent and severe coughing spells

Nausea (a)

1. I seldom feel any nausea at all
2. I am nauseous once in awhile
3. I am often nauseous
4. I am usually nauseous
5. I suffer from nausea almost continually

Nausea (b)

1. When I do have nausea, it is very mild
2. When I do have nausea, it is mildly distressing
3. When I do have nausea, I feel pretty sick
4. When I do have nausea, I feel very sick
5. When I do have nausea, I am as sick as I could possibly be

Depression

1. I seldom feel sad and depressed
2. I am sad and depressed once in a while
3. I am often sad and depressed
4. I am usually sad and depressed
5. I am sad and depressed almost all the time

Appendix V Compliance Questionnaire

Please answer the question below about how often you took your study treatment during the past cycle.

Check only one box that reflects your response.

Over the past week, I took my study supplement:

- Always or almost always
- Usually
- Occasionally
- Rarely
- Never or almost never

Patient reported weight: _____ Unit of measure: (check one) _____ lbs. _____ kg

Appendix VI Nurse/CRA Phone Worksheet**Phone Contact Guide**

NOTE: This should serve only as a guide to collect information while on the phone with the patient and does not replace any data forms which are required to be filled out. Do not fill out and submit this form, rather submit the data forms using the RDE system.

1. Call patient on day 2 of cycle 1 to reinforce daily questionnaire completion and answer any questions they may have. If day 2 falls on a weekend or holiday, you may call the patient on the next business day. .
2. Call patient on day 2 of cycle 2 and day 2 of cycle 3 to assess compliance and answer questions below. Note: phone calls are only required for patients not returning to the accruing institution for monthly therapy/assessment. Patients returning to the accruing institution for monthly therapy should be seen and assessed in person. Patients not returning to the accruing institution for therapy should be assessed via phone.

1. Items to document include:

- Date of phone call.
- Study cycle.
- Compliance: Has the participant completed the questionnaire booklet each week (always, usually, rarely, never)? If not always, document reason(s) and reinforce weekly booklet completion. If never, document reason(s) in the Patient Questionnaire Booklet Compliance Form and reinforce weekly booklet completion.
- Side effects

Abdominal pain

Bloating

Diarrhea

Baseline number of stools per day

Flatulence

Nausea

Vomiting

Fatigue

Wound infection

Wound complication

Wound dehiscence

- Has the patient been taking the agent (Always or almost always; Usually; Occasionally; Rarely; Never or almost never)?

4. Reinforce compliance with booklet and remind participant to return booklet to study staff at their next appointment or in the envelope provided at the end of each 4 weeks.

5. Reinforce completion of questionnaires. NOTE: if patient decides to stop study early, ask them to fill out the questionnaires at the end of the booklet and return in the envelope provided.

7. Items to document include:

- Date of phone call.
- Study cycle.
- Patient reported weight. (lbs/kg)
- Has cancer therapy started (yes/no). If yes, chemo/RT/hormonal/other, specify-List start date of each.
- Compliance questionnaire

